7.4 Efficacy Analysis

All efficacy analyses will be performed on the mITT population and PP population using the methods described below. Regression models will include all eligible subjects for the respective analysis, from the 3 treatment arms.

- *Primary Analysis*: Includes data for all subjects in the respective population (mITT/PP)
- *Sub-Analysis*: Excludes data collected on/after date of first on-treatment rescue medication use through the end of the study.
 - For WI-NRS/AI-NRS endpoints, excludes data from *week* of first on-treatment rescue medication use.
- *Non-Responder Imputation (NRI) Analysis*: Subjects who discontinue treatment early or who take on-treatment rescue medications will be imputed as a non-responder for assessments that occur on/after date of discontinuation/on-treatment rescue medication use through the end of the study.

STATISTICAL ANALYSIS PLAN

Version 3.0 12-Jan-22

- For WI-NRS/AI-NRS endpoints, excludes data from *week* of discontinuation/first on-treatment rescue medication use.
- Subjects who discontinue early should have at least one treatment-emergent adverse event (TEAE) leading to discontinuation in order to have their data imputed for NRI analysis.

| Efficacy Analyses | lyses | A | cacy | Effi |
|-------------------|-------|---|------|------|
|-------------------|-------|---|------|------|

| Measure | Endpoints | Analysis |
|--------------------|---|--|
| WI-NRS/ AI-NRS* | Mean Change from Baseline | Primary Primary/Sensitivity Sub-Analysis Sub-Analysis/Sensitivity |
| WI-NRS/ | Improvement | Primary Primary/Sensitivity Sub-Analysis Sub-Analysis/Sensitivity NRI NRI |
| AI-NKS* | (4-Point, Any) | 6. NRI/Sensitivity |
| 5D | Mean Change from Baseline | 2. Sub-Analysis |
| EASI | Mean Change from Baseline | Primary Sub-Analysis |
| EASI | Improvement (≥50%, ≥75%, ≥90%) | 1. Primary 2. Sub-Analysis 3. NRI |
| IGA | Mean Change from Baseline | 1. Primary 2. Sub-Analysis |
| IGA | Improvement (2-Point to Clear/Almost Clear, Clear/Almost Clear, Any) | Primary Sub-Analysis NRI |
| POEM | Mean Change from Baseline | Primary Sub-Analysis |

*WI-NRS/AI-NRS analyses require at least 1 diary entry per week to calculate the weekly average, except for the sensitivity analyses, where at least 4 diary entries per week are required.

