 - Footnote [3] will be same as in 14.2.2.3.8, except changing "WI-NRS" to "AI-NRS"

Table 14.2.2.5.1 Proportion of Subjects with ≥4 Point Improvement in WI-NRS from Baseline to Weeks 1 Through 8 – Primary Analysis (mITT Population)

| Visit | Statistic Type | Statistic | B244 O.D. 5.0 (N=xx) | B244 O.D. 20.0 (N=xx) | Pooled B244 (N=xx) | Vehicle (N=xx) |
|-------------|----------------|----------------------------------|------------------------------|------------------------------|------------------------------|------------------------------|
| Week 1 | Logistic [1,2] | n/N (Proportion %) [3] 95% CI | xx/xx (xx.x) (xx.x, xx.x) | xx/xx (xx.x) (xx.x, xx.x) | xx/xx (xx.x) (xx.x, xx.x) | xx/xx (xx.x) (xx.x, xx.x) |
| Papart for | v. Vehicle | Odds Ratio (95% CI) p-value | x.xx (x.xx, x.xx) x.xxxx | x.xx (x.xx, x.xx) x.xxxx | x.xx (x.xx, x.xx) x.xxxx | N/A N/A |
| Weeks 2 – 8 | 20.0 v 5.0 | Odds Ratio (95% CI) p-value | N/A N/A | x.xx (x.xx, x.xx) x.xxxx | N/A N/A | N/A N/A |

[1] Logistic regression model contains treatment group as the explanatory variable. At least one WI-NRS daily score is reported between Days -7 and -1 and for the corresponding week. All subjects who meet mITT criteria are included and no data is excluded based on rescue medication use.

[2] Treatment response is improvement by \geq 4 Points in WI-NRS score (i.e., decrease in WI-NRS score by at least 4 points from Baseline to Post-Baseline visit).

[3] n is the number of subjects who have improved at that visit. N is the number of subjects with data at that visit, regardless of improvement status.

Source: Listing XXXX

PROGRAM NAME: XXXXXXXXXX

DATE: HH:MM/DDMMMYYYY

- Repeat for 14.2.2.5.2 Proportion of Subjects with ≥4 Point Improvement in WI-NRS from Baseline to Weeks 1 Through 8 Primary Analysis Sensitivity for mITT Population
 - o Footnote [1] will be same as in 14.2.2.5.1, except changing "one WI-NRS daily score is" to "four WI-NRS daily scores are"
 - Footnotes [2,3] will be same as in 14.2.2.5.1
- Repeat for 14.2.2.5.3 Proportion of Subjects with ≥4 Point Improvement in WI-NRS from Baseline to Weeks 1 Through 8 Sub-Analysis for mITT Population
 - Footnote [1] will be same as in 14.2.2.5.1, except changing the last statement to "Excludes data collected from the week of first on-treatment rescue medication use through the end of the study. Data collected prior to the week of first on-treatment rescue medication use will be included."

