 - Footnotes [2,3] will be same as in 14.2.2.5.1
- Repeat for 14.2.2.5.4 Proportion of Subjects with ≥4 Point Improvement in WI-NRS from Baseline to Weeks 1 Through 8 Sub-Analysis Sensitivity for mITT Population
 - Footnote [1] will be same as in 14.2.2.5.1, except changing "one WI-NRS daily score is" to "four WI-NRS daily scores are" and changing the last statement to "Excludes data collected from the week of first on-treatment rescue medication use through the end of the study. Data collected prior to the week of first on-treatment rescue medication use will be included."
 - Footnotes [2,3] will be same as in 14.2.2.5.1
- Repeat for 14.2.2.5.5 Proportion of Subjects with ≥4 Point Improvement in WI-NRS from Baseline to Weeks 1 Through 8 Non-Responder Imputation (NRI) Analysis for mITT Population
 - Footnote [1] will be same as in 14.2.2.5.1, except changing the last statement to "Subjects who discontinue treatment early or who take on-treatment rescue medications are imputed as non-responders."
 - Footnotes [2,3] will be same as in 14.2.2.5.1
- Repeat for 14.2.2.5.6 Proportion of Subjects with ≥4 Point Improvement in WI-NRS from Baseline to Weeks 1 Through 8 Non-Responder Imputation (NRI) Analysis Sensitivity for mITT Population

- Footnote [1] will be same as in 14.2.2.5.1, except changing "one WI-NRS daily score is" to "four WI-NRS daily scores are" and changing the last statement to "Subjects who discontinue treatment early or who take on-treatment rescue medications are imputed as non-responders."
- Footnotes [2,3] will be same as in 14.2.2.5.1
- Repeat for 14.2.2.5.7 Proportion of Subjects with ≥4 Point Improvement in WI-NRS from Baseline to Weeks 1 Through 8 Primary Analysis for PP Population
 - Footnote [1] will be same as in 14.2.2.5.1, except changing the last statement to "All subjects who meet PP criteria are included."
 - Footnotes [2,3] will be same as in 14.2.2.5.1
- Repeat for 14.2.2.5.8 Proportion of Subjects with ≥4 Point Improvement in WI-NRS from Baseline to Weeks 1 Through 8 Primary Analysis Sensitivity for PP Population
 - Footnote [1] will be same as in 14.2.2.5.1, except changing "one WI-NRS daily score is" to "four WI-NRS daily scores are" and changing the last statement to "All subjects who meet PP criteria are included."
 - Footnotes [2,3] will be same as in 14.2.2.5.1
- Repeat for 14.2.2.5.9 Proportion of Subjects with \geq 4 Point Improvement in WI-NRS from Baseline to Weeks 1 Through 8 Sub-Analysis for PP Population

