 Footnotes [1,2,3] will be same as in 14.2.2.5.3, except changing "WI-NRS" to "AI-NRS"
- Repeat for 14.2.2.7.4 Proportion of Subjects with ≥4 Point Improvement in AI-NRS from Baseline to Weeks 1 Through 8 Sub-Analysis Sensitivity for mITT Population

 Footnotes [1,2,3] will be same as in 14.2.2.5.4, except changing "WI-NRS" to "AI-NRS"
- Repeat for 14.2.2.7.5 Proportion of Subjects with ≥4 Point Improvement in AI-NRS from Baseline to Weeks 1 Through 8 Non-Responder Imputation (NRI) Analysis for mITT Population
 - Footnotes [1,2,3] will be same as in 14.2.2.5.5, except changing "WI-NRS" to "AI-NRS"
- Repeat for 14.2.2.7.6 Proportion of Subjects with ≥4 Point Improvement in AI-NRS from Baseline to Weeks 1 Through 8 Non-Responder Imputation (NRI) Analysis Sensitivity for mITT Population
 - Footnotes [1,2,3] will be same as in 14.2.2.5.6, except changing "WI-NRS" to "AI-NRS"
- Repeat for 14.2.2.7.7 Proportion of Subjects with ≥4 Point Improvement in AI-NRS from Baseline to Weeks 1 Through 8 Primary Analysis for PP Population

 Footnotes [1,2,3] will be same as in 14.2.2.5.7, except changing "WI-NRS" to "AI-NRS"
- Repeat for 14.2.2.7.8 Proportion of Subjects with ≥4 Point Improvement in AI-NRS from Baseline to Weeks 1 Through 8 Primary Analysis Sensitivity for PP Population
 - Footnotes [1,2,3] will be same as in 14.2.2.5.8, except changing "WI-NRS" to "AI-NRS"
- Repeat for 14.2.2.7.9 Proportion of Subjects with ≥4 Point Improvement in AI-NRS from Baseline to Weeks 1 Through 8 Sub-Analysis for PP Population
 o Footnotes [1,2,3] will be same as in 14.2.2.5.9, except changing "WI-NRS" to "AI-NRS"
- Repeat for 14.2.2.7.10 Proportion of Subjects with ≥4 Point Improvement in AI-NRS from Baseline to Weeks 1 Through 8 Sub-Analysis Sensitivity for PP Population

 Footnotes [1,2,3] will be same as in 14.2.2.5.10, except changing "WI-NRS" to "AI-NRS"
- Repeat for 14.2.2.7.11 Proportion of Subjects with ≥4 Point Improvement in AI-NRS from Baseline to Weeks 1 Through 8 Non-Responder Imputation (NRI) Analysis for PP Population
 - Footnotes [1,2,3] will be same as in 14.2.2.5.11, except changing "WI-NRS" to "AI-NRS"
- Repeat for 14.2.2.7.12 Proportion of Subjects with ≥4 Point Improvement in AI-NRS from Baseline to Weeks 1 Through 8 Non-Responder Imputation (NRI) Analysis Sensitivity for PP Population
 - Footnotes [1,2,3] will be same as in 14.2.2.5.12, except changing "WI-NRS" to "AI-NRS"

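### SAP 7.4 contradicts itself on non-responder imputation for WI-NRS and AI-NRS responders, and the NRI table shells let imputed failures fall out of the denominator

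*SAP*

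**What the plan says.** SAP section 7.4 lists three handlings of the data: primary, sub-analysis and NRI.

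- **NRI, parent bullet.** Subjects who stop treatment early or use on-treatment rescue "will be imputed as a non-responder for assessments that occur on/after date of discontinuation/on-treatment rescue medication use through the end of the study".
- **NRI, sub-bullet for WI-NRS/AI-NRS.** "excludes data from *week* of discontinuation/first on-treatment rescue medication use". No replacement value is given.
- **NRI, condition on discontinuers.** They need "at least one treatment-emergent adverse event (TEAE) leading to discontinuation in order to have their data imputed for NRI analysis".
- **Sub-analysis, sub-bullet.** "For WI-NRS/AI-NRS endpoints, excludes data from *week* of first on-treatment rescue medication use".

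The shells in SAP Appendix A, section 1.1.2, give the two analyses different footnotes. In the WI-NRS NRI tables (14.2.2.5.5 and 14.2.2.5.6, and the per-protocol versions), the last sentence of footnote [1] becomes "Subjects who discontinue treatment early or who take on-treatment rescue medications are imputed as non-responders". The AI-NRS NRI table takes this over: its footnotes "will be same as in 14.2.2.5.5, except changing" the scale name. The sub-analysis tables instead carry "Excludes data collected from the week of first on-treatment rescue medication use through the end of the study".

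The rest of footnote [1] is unchanged in the NRI shells. It asks for at least one daily score in the baseline week and in the week analysed, or four in the sensitivity version. Footnote [3] is also kept: "N is the number of subjects with data at that visit, regardless of improvement status". The note under the section 7.4 table repeats the diary minimum. Section 6.5.3 sets a weekly average with fewer than four entries to missing in the sensitivity analysis, and section 7.6 provides no other handling of missing efficacy data.

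**The concern.** NRI exists to keep treatment failures in the denominator and count them as failures. Two features of the text work against that for the itch responders.

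First, within one short list the same verb has to mean dropping data in the sub-analysis and setting data to non-response under NRI. The specific sub-bullet is the one a programmer would naturally follow for these endpoints. Followed literally, it removes failures and makes the NRI table close to a repeat of the sub-analysis.

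Second, even a programmer who imputes meets a diary-in-the-week condition and an N limited to subjects with data. A subject who left the study after an adverse event may have no diary in Week 4, and the parent bullet reaches only assessments that take place.

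The proportion with at least a 4-point WI-NRS improvement at Week 4 is the first secondary endpoint listed in SAP section 3.2.2. Protocol section 8.14.1 permits rescue up to 7 days per month, so some rescue use must be expected.

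**Working it through.** The plan states no figure to reproduce. The check is a comparison of texts, followed by an illustration on assumed rates.

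**Step 1. Which reading does the plan as a whole support?**

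| Place | Handling of itch responders after the event |
|---|---|
| SAP 7.4, NRI parent bullet | Imputed |
| SAP 7.4, NRI sub-bullet for WI-NRS/AI-NRS | Excluded, no value given |
| SAP 7.4, NRI adverse-event condition | Imputed, for discontinuers who meet it |
| NRI shells, footnote [1] | Imputed |
| Sub-analysis shells, footnote [1] | Excluded |
| SAP addendum, Request 1 | NRI described as imputation; worst-value imputation built as its parallel |

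The sub-bullet is the exception. Its likely purpose is to move the boundary from the event date to the event week, because the endpoint is a weekly average.

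**Step 2. Do the shells then deliver imputation?** Not for everyone. A subject due for imputation but with no diary entry in the week (fewer than four in the sensitivity version) fails the retained part of footnote [1]. Such a subject has no data for footnote [3], and section 7.6 supplies nothing further. Whether this subject counts as a non-responder or is absent from N is left open, and on the literal footnotes the subject is absent.

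**Step 3. Size within an arm.** Let p be the response rate among subjects without an event, f the share of failures due for imputation, and m the share of those failures who drop out of N. Then

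reported rate = p(1 − f) / (1 − f·m).

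- m = 0 (NRI as intended): p(1 − f).
- m = 1 (exclusion): p.

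The documents give no values of p or f, so these are assumptions:

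- p = 0.40, f = 0.20: exclusion 40%; NRI 0.40 × 0.80 = 32%.
- p = 0.40, f = 0.30: exclusion 40%; NRI 0.40 × 0.70 = 28%.

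If only some failures lack diaries, the result lies between the two.

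**Step 4. Size between arms.** Assume p = 30% on active and 20% on vehicle. Exclusion gives 30% against 20% whatever the failure shares, with odds ratio (0.30/0.70)/(0.20/0.80) = 1.71. NRI gives:

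| Failures, active / vehicle | NRI rates | Odds ratio |
|---|---|---|
| 10% / 10% | 27% v 18% | (0.27/0.73)/(0.18/0.82) = 1.68 |
| 10% / 20% | 27% v 16% | (0.27/0.73)/(0.16/0.84) = 1.94 |
| 20% / 10% | 24% v 18% | (0.24/0.76)/(0.18/0.82) = 1.44 |

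With equal failure shares the contrast hardly changes. With unequal shares it moves, and the direction depends on which arm fails more.

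**The case against.** The strongest reply is that the plan, read whole, imputes. The parent bullet, the adverse-event condition, footnote [1] of every itch NRI shell and the addendum all say so, and the sub-analysis shells carry a visibly different footnote. This stands. A reader might infer from the sub-bullet alone that the sponsor chose exclusion in place of imputation, so that the planned NRI is an analysis of subjects who did not fail. The documents do not support that inference.

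A second reply is that footnote [3] and the diary condition are boilerplate. Footnote [3] also sits in the EASI and IGA NRI shells. Both appear in the addendum's LOCF responder shell, beside a statement that missing Week 4 values are imputed. This stands in part. Those lines do not show an intention to remove imputed subjects, and rescue users who keep entering daily scores would meet the diary condition. They still leave subjects with too few diaries without a defined status, and boilerplate is what gets programmed.

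A third reply is that little hangs on it: NRI is supplementary, the responder endpoints' own primary analysis keeps all data despite rescue, and section 7.4 calls secondary p-values exploratory. All true. This limits the importance of the point but does not settle how the tables should be produced.

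**Conclusion.** The rule is wrong as written. One sub-bullet contradicts the imputation rule it belongs to, and the retained footnotes can drop rescued subjects, or discontinuers meeting the adverse-event condition, from the denominator even when imputation is applied.

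Where that happens, the response rate in an arm is overstated, at most p in place of p(1 − f): 40% against 32% for an assumed 20% failure share, or against 28% for 30%. The size rests entirely on assumed rates. It would be wrong to conclude that the treatment effect is inflated: the contrast can move up, down or barely at all, depending on the balance of failures. The primary ANCOVA on mean WI-NRS change does not use NRI and is untouched. The matter should be corrected before the NRI tables are produced, but it affects only supplementary analyses of exploratory responder endpoints.

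**What to change.** Replace the WI-NRS/AI-NRS sub-bullet under NRI in SAP section 7.4 with: *For WI-NRS/AI-NRS, weekly response is set to non-response from the week of first on-treatment rescue use, or of discontinuation meeting the TEAE condition, onward, whether or not diaries exist.*

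In the NRI shells, make three changes:

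- Footnote [1]: waive the diary-in-the-week condition for imputed subjects, in both the one-entry and four-entry versions.
- Footnote [1]: state the adverse-event condition on discontinuers, which section 7.4 imposes and the footnote now omits.
- Footnote [3]: define N as subjects with data at that week plus all imputed subjects.

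This definition of N leaves the adverse-event condition in force and does not force a decision on subjects missing for other reasons. Setting N to the whole analysis population would need such a decision, because section 7.6 gives those subjects no status.

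The cost is one sentence and the footnotes of shells 14.2.2.5.5, 14.2.2.5.6, 14.2.2.5.11 and 14.2.2.5.12. The any-improvement and AI-NRS NRI tables inherit from these by cross-reference. No new data are needed.

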7.6 Handling of Dropouts or Missing Data

To account for missing daily diary entries for WI-NRS and AI-NRS, the average score for a week will be presented, where at least one score or four scores must be collected in a week for the primary and sensitivity analyses, respectively.

No other accommodations will be made for missing data other than those discussed in sections 6.5.7 and 6.5.9.

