A Phase II, Randomized, Double-Blind, Vehicle Controlled Study of the Efficacy, Safety, and Tolerability of B244 Topical Spray for the Treatment of Pruritus in Adults with a History of Atopic Dermatitis

Sponsor:

AOBiome, LLC [name]

ADDENDUM TO SAP v3.0

Version 1.0 22-Apr-22

ADDENDUM TO SAP REVIEW AND APPROVAL

This Addendum to Statistical Analysis Plan v3.0 (12Jan2022) has been prepared in accordance with team reviewers' specifications.

| Prepared by: [name]. Signing Reason: 1 am the author of this document Signing Time: 03 May 2022 4:44:40 AM PDT F18BA 1C2EF7C48A4B775BE54652AC840 | 03 May 2022 |
|--|------------------|
| [name], Bio-Statistician | Date |
| Sponsor Review: | 05 May 2022 |
| [name], Bio-Statistician | Date 05 May 2022 |
| [name], VP of Clinical Operations | Date |

ADDENDUM TO SAP v3.0

Version 1.0 22-Apr-22

Table of Contents

| 1 | Background and Purpose | . 4 |
|---|--|-----|
| 2 | Request 1: Worst Case Analysis | . 4 |
| 3 | Request 2: Intention-to-Treat Analysis | . 5 |
| 4 | List of Tables | . 6 |
| 5 | Table Shells | . 8 |

ADDENDUM TO SAP v3.0

Version 1.0 22-Apr-22

1 Background and Purpose

The purpose of this addendum to the final Statistical Analysis Plan (SAP) for the PRB244-01 study (v3.0 dated 12Jan2022) is to describe additional statistical analyses that will be performed in order to address requests by the FDA made on 27Mar2022. These requests are detailed in the sections below.

2 Request 1: Worst Case Analysis

FDA Request: You proposed the non-responder imputation analysis in which subjects who discontinue treatment early or who take on-treatment rescue medications will be imputed as a non-responder. Similar to the non-responder imputation analysis, we recommend that you provide additional analyses on the primary efficacy endpoint and relevant efficacy endpoints in which the underlying score-based variable values (e.g., WI-NRS, AI-NRS, IGA, etc.), are imputed with the worst score on/after date of first rescue medication use through the end of the study.

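### The SAP and Addendum limit imputation of early discontinuers to those with a TEAE leading to discontinuation, but the NRI and WOCF table footnotes print no such limit, and the footnotes leave it unclear whether imputed dropouts count in N

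*SAP*

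**What the plan says.** SAP 7.4 opens its NRI definition broadly: "Subjects who discontinue treatment early or who take on-treatment rescue medications will be imputed as a non-responder", and this applies "for assessments that occur on/after date of discontinuation/on-treatment rescue medication use through the end of the study". A sub-bullet for WI-NRS and AI-NRS excludes data from the week of discontinuation or first rescue use. The last sub-bullet then narrows the rule: "Subjects who discontinue early should have at least one treatment-emergent adverse event (TEAE) leading to discontinuation in order to have their data imputed".

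Addendum Section 2 describes WOCF as a parallel to NRI and has values missing through early discontinuation replaced. It imposes two conditions on discontinuers: a TEAE that led to discontinuation, and discontinuation before the Week 4 visit. The agency request reproduced there describes the proposed NRI as one "in which subjects who discontinue treatment early or who take on-treatment rescue medications will be imputed as a non-responder", with no TEAE condition.

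In SAP Appendix A (1.1.2), footnote [1] of the NRI tables ends: "Subjects who discontinue treatment early or who take on-treatment rescue medications are imputed as non-responders". In Addendum Section 5, footnote [3] of the WOCF tables says that values missing through dropout are filled by WOCF. No limit is printed in either place.

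On the denominator, the NRI tables take footnote [3] unchanged from the base responder shells: "N is the number of subjects with data at that visit, regardless of improvement status". The WI-NRS and AI-NRS NRI tables also keep this part of footnote [1]: "At least one WI-NRS daily score is reported between Days -7 and -1 and for the corresponding week".

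**The concern.** A reader of an NRI table will assume that every early treatment discontinuer was counted as a failure, because the footnote says so. Under the text rule, a subject who simply leaves for lack of benefit, with no TEAE recorded as the cause and no on-treatment rescue use, is not imputed. That is the kind of subject NRI is normally meant to catch. The WOCF tables have the same problem, and those were added in answer to an agency request.

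The second issue is counting. If N means only subjects with observed data, a dropout with nothing recorded at the visit disappears from the table even where imputation is intended. At stake are the mITT NRI tables for secondary and exploratory responder endpoints and the Addendum sensitivity tables.

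**Working it through.** **Rule, side by side**

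| Place | TEAE limit stated? | Pre-Week 4 limit stated? |
|---|---|---|
| SAP 7.4, last NRI sub-bullet | Yes | No |
| NRI footnote [1]: Table 14.2.2.5.5 (WI-NRS, carried to AI-NRS) and Table 14.2.2.13.3 (EASI, carried to IGA) | No | No |
| Addendum Section 2, WOCF text | Yes | Yes |
| WOCF footnote [3]: Tables 14.2.2.2a, 14.2.2.3.4a, 14.2.2.10.2a | No | No |

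The missing pre-Week 4 limit matters where Week 8 is reported: Tables 14.2.2.3.4a and 14.2.2.10.2a and those that inherit from them.

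**Denominator, side by side**

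| Shell | N limited to subjects with data? | Diary score needed in that week? | Imputation stated? |
|---|---|---|---|
| NRI, WI-NRS/AI-NRS | Yes | Yes | Yes |
| NRI, EASI/IGA | Yes | No | Yes |
| LOCF responder, WI-NRS (14.2.2.5.13) | Yes | Yes | Yes |
| LOCF responder, EASI-75 (14.2.2.14.7) | Yes | No | Yes |
| WOCF MMRM, WI-NRS/AI-NRS (14.2.2.3.4a) | No N footnote | Yes | Yes |
| WOCF ANCOVA (14.2.2.2a) | No N footnote | Baseline week only | Yes |

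The NRI and LOCF responder shells pair imputation with an N that, read literally, leaves out the imputed subjects without data. The WOCF MMRM shell pairs imputation with the diary condition.

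**Size**

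Inputs from SAP 7.1: 576 enrolled, 160 evaluable per group, 16.7% dropout. The plan's figure reproduces: 480/(1 − 0.167) = 576.2, and 576/3 = 192 per arm. Planned dropouts per arm are 192 − 160 = 32, and 32/192 = 16.7%.

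Assumptions: all 32 are in mITT, lack Week 4 data and used no rescue; 48 of the other 160 respond. Let t be the number of the 32 with a qualifying TEAE, and count imputed subjects in N:

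- All discontinuers imputed: 48/192 = 25.0%.
- TEAE rule, 48/(160 + t): t = 0 gives 30.0%; t = 16 gives 48/176 = 27.3%; t = 32 gives 25.0%.
- If N instead counts observed data only: 48/160 = 30.0%, whatever t is.

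These figures are not a ceiling. If the 32 had Week 4 data that were kept, 16 of them responded and none was imputed, the rate would be (48 + 16)/192 = 33.3% against 25.0%.

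**Direction within an arm.** A discontinuer who is not imputed either drops out of the denominator or keeps an observed result. Neither can take the rate below the all-discontinuer value.

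**Direction between arms.** Assume 64 responders on active and 48 on vehicle among 160 each. All imputed: 64/192 − 48/192 = 8.3 points. TEAE rule with 12 coded on active and 2 on vehicle: 64/172 − 48/162 = 7.6 points. With 2 and 8 coded: 64/162 − 48/168 = 10.9 points.

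**The case against.** The TEAE limit appears deliberate. A broad sentence followed by a condition is a rule with a qualifier, so SAP 7.4 does not contradict itself, and the Addendum repeats the condition after the agency's request. The agency's sentence is a short description of the proposal and does not define the sponsor's rule. The limit has some rationale: Protocol 13.1 counts worsening of a pre-existing condition as an AE, and rescue users are imputed separately. All of this stands. It shows which rule probably governs, but it does not make footnotes that omit the rule accurate. Nor does it reach the subject who leaves for lack of benefit without a coded TEAE.

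On N, the sponsor can answer that an imputed value counts as data. The LOCF shells support that answer: they use the same N wording while stating that all ITT subjects are included and missing Week 4 values are imputed. A reader might infer that imputed dropouts are definitely left out of N. The documents do not support that; the point is an ambiguity. SAP 7.6 does not resolve it either. Its statement, "No other accommodations will be made for missing data other than those discussed in sections 6.5.7 and 6.5.9", would rule out NRI altogether if read literally, so it says nothing about how NRI counts N.

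The consequence is limited. Secondary and exploratory p-values are exploratory by SAP 7.4, and WOCF is a sensitivity analysis.

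**Conclusion.** The mismatch between text and footnotes is established on the wording. Tables produced as written would misdescribe who was imputed, and the text rule lets some discontinuers escape an analysis labelled non-responder imputation. The denominator issue is an unresolved ambiguity.

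The illustrated difference is 30.0% against 25.0% per arm. Only 192 and 16.7% come from the documents; responder counts, TEAE counts and the assumption that all 32 are missing at Week 4 are mine. The 32 is generous in one respect: mITT requires a post-baseline on-site visit, and some dropout will fall after Week 4. A reader might take the ratio of 1.20 as a maximum, or expect early-termination data to shrink the gap. Neither follows, because observed responses in discontinuers who are not imputed can widen it. SAP 7.4 also does not say whether diary data after discontinuation are kept for such subjects.

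A reader might also infer that the primary result is at risk. It is not: the ANCOVA in Table 14.2.2.1 uses no such imputation. Nor should the ITT LOCF analysis be relied on as a safeguard. It carries the same N wording, can carry an earlier response forward, and addresses Week 4 only.

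**What to change.** 1. State one rule in text and footnotes. Either remove the TEAE condition from SAP 7.4 and Addendum Section 2, or keep it, print it in every NRI and WOCF footnote, and add an all-discontinuer NRI as a sensitivity analysis.
2. In the NRI and LOCF responder tables, define N as subjects with observed or imputed data at the visit. Waive the corresponding-week diary condition for imputed subjects there and in the WI-NRS/AI-NRS WOCF MMRM footnotes.
3. State in SAP 7.4 whether diary data after discontinuation are kept or excluded for discontinuers who are not imputed.
4. Add the Addendum's rule on dropout after the Week 4 visit to the WOCF footnotes of tables that report Week 8: 14.2.2.3.4a, 14.2.2.10.2a and those inheriting from them.

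The cost is a few sentences, a derivation flag and edits to the base shells, which pass to the parallel tables, plus one sensitivity analysis if the TEAE limit is kept. Reported response rates may be slightly lower.
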